13. STATISTICAL CONSIDERATIONS

13.1 Statistical and analytical plans

The material of this section is the basis for the Statistical Analysis Plan of this study. This plan may be revised during the study to accommodate Clinical Trial Protocol Amendments and to make changes to adapt to unexpected issues in study execution and data that affect planned analyses. These revisions will be based on blinded review of the study and data, and a final plan will be issued prior to data lock.

13.2 Determination of sample size

Based on the targeted population for the study, 3% is considered a reasonable assumption for the yearly event rate in the placebo group. Assuming recruitment over a 17 month period, and a total study duration of 50 months, 8,500 patients per group (total 17,000) will give a power of 90% (two-sided test, at the 5% significance level) to the trial to show an overall 15% risk reduction (or equivalently no effect the first year, followed by a 25% risk reduction in subsequent years). This corresponds to approximately 1,600 events.

These computations allow for a 10% annual rate of treatment discontinuation.

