11.2 Follow-up procedures after withdrawal

Patients who prematurely discontinue study drug are not to be replaced.

All randomized patients must be followed up according to the study flowchart until study end date or death, regardless of whether they discontinued study drug prematurely or not. Any event occurring after early study drug discontinuation will be recorded up through the study end date.

In case of study drug discontinuation (temporary or permanent) due to an adverse event, such patients will be closely monitored until the resolution or stabilization of this adverse event. This may mean that follow-up will continue after the patients have completed the study follow-up. Although data on that adverse event will continue to be captured, even

beyond the last visit, for new efficacy or safety events, only those that occur up through the last visit should be recorded.

In case of written withdrawal of consent (WOC) for follow-up visits, and unless otherwise stated by the patient in the informed consent form, Investigators will be encouraged to get information from the general practitioner, any other physician, or other medical-care provider, in order to follow the medical status of the patients (especially when they withdraw their consent after having experienced an AE/SAE or an efficacy endpoint). Investigators will also be expected to try as much as possible to re-contact those patients at the end of the trial, in order to obtain at least their vital status (dead or alive), as well as their stroke or MI status if possible, and thus avoid lost to follow-up for the efficacy assessment.

For patients considered lost to follow-up, the CRF must be completed up to the last visit performed.

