13.7.1.2.3 Main statistical model and adjustment for covariates

For the primary analysis, all adjudicated events occurring from randomization to the study end date (inclusive) will be counted, including events occurring after early permanent discontinuation of study drug. The proportion of patients remaining event-free over time will be displayed in the form of survival curves using the Kaplan-Meier method and analyzed (primary analysis) using a two-sided log-rank test. Statistical significance will be claimed if the computed p-value is equal to or less than 0.05.

The number and percentage (crude rate) of patients experiencing a primary endpoint will be summarized.

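### Section 13.2 calls a one-year lag followed by a 25% reduction equivalent to 15% overall at 90% power; with 10% a year stopping drug for good, the lag scenario has about 84-85% power

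*Protocol*

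**What the plan says.** Section 13.2 assumes that "3% is considered a reasonable assumption for the yearly event rate in the placebo group". On timing it reads: "Assuming recruitment over a 17 month period, and a total study duration of 50 months". From these, "8,500 patients per group (total 17,000) will give a power of 90% (two-sided test, at the 5% significance level") to "show an overall 15% risk reduction (or equivalently no effect the first year, followed by a 25% risk reduction in subsequent years"). It adds: "This corresponds to approximately 1,600 events", and closes with: "These computations allow for a 10% annual rate of treatment discontinuation".

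Two other places decide what discontinuation does to the comparison. Section 11.2 says: "All randomized patients must be followed up according to the study flowchart until study end date or death". Section 13.7.1.2.3 counts all adjudicated events up to the study end date, "including events occurring after early permanent discontinuation of study drug". Stopping drug therefore dilutes the treatment effect; it does not censor the patient.

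Section 13.2 does not say whether 15% and 25% are net or on-drug effects, when discontinuation starts, whether it is permanent, or what effect remains after stopping.

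**The concern.** One power figure is attached to two effect scenarios and one discontinuation allowance. If the two scenarios are equivalent, the lag scenario must dilute to a hazard ratio of about 0.85 once discontinuation is applied. On the plainest reading it dilutes further. On the other plain reading, with no discontinuation, it falls well short of that dilution.

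At stake is the type II error reported for the primary endpoint. Under the lag scenario with permanent stopping and full loss of effect, the chance of missing the effect is about 15-16%, against the 10% that the section implies.

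**Working it through.** **Inputs** (Section 13.2): placebo rate 3% a year; 8,500 per arm; 17 months of recruitment; 50 months in total, so follow-up of 33 to 50 months; two-sided 5%; 10% annual discontinuation. Assumed here: uniform accrual and no loss to follow-up. The ranges cover 3% read as a hazard or as an annual probability (λ = 0.03 or −ln 0.97 = 0.0305), and 10% likewise.

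**1. Events needed for HR 0.85 at 90% power.** Schoenfeld: 4(1.960 + 1.282)²/(ln 0.85)² = 1,592. Freedman: (1.960 + 1.282)² × (1.85/0.15)² = 1,599. Both match the stated figure of about 1,600.

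**2. Events the design yields.** Per arm, with time in years,

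E = 8,500 × [1 − (e^(−2.75λ) − e^(−4.167λ))/(1.417λ)].

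Placebo: 837 to 849. Rimonabant at 0.85λ: 717 to 728. Total: 1,554 to 1,577. Power = Φ(½√D × |ln HR| − 1.96). At D = 1,577: ½ × 39.71 × 0.1625 − 1.96 = 1.27, or 90%. At D = 1,554: 89%. The headline figure is reproduced with 15% as the net effect.

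**3. Lag scenario without stopping.** First-year events are 8,500 × 0.03 = 255 per arm, 510 in all, out of about 1,554. The share after year 1 is 1 − 510/1,554 = 0.672. Average HR = exp(0.672 × ln 0.75) = 0.824.

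**4. Lag scenario with stopping.** Let w(t) = 0.9^t be the share still on drug. The rimonabant-arm hazard is λ in year 1 and λ[1 − 0.25 w(t)] afterwards. By hand: follow-up time after year 1 is centred at about 2.26 years, where w = 0.9^2.26 = 0.788 and HR = 1 − 0.25 × 0.788 = 0.803. With 1 − 510/1,585 = 0.678 of events after year 1, the average HR is exp(0.678 × ln 0.803) = 0.86.

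Numerical integration of the expected log-rank score and variance over follow-up gives:

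| Scenario | Events | Average HR | Power |
|---|---|---|---|
| Net HR 0.85 throughout | 1,554-1,577 | 0.850 | 89-90% |
| 15% on drug, 10%/yr stopping | 1,573-1,597 | 0.873-0.874 | 76-77% |
| Lag, then 25%, no stopping | 1,532-1,554 | 0.824 | 96-97% |
| Lag, then 25% on drug, 10%/yr stopping from randomization, full loss of effect | 1,560-1,585 | 0.859-0.861 | 84-85% |

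A simulation of 3,000 trials of the last row gave 85.4% (standard error about 0.6 points).

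**5. What moves the last row.** All of the following are assumptions that Section 13.2 does not state:
- Losing 10 percentage points of the arm each year: 82-83%.
- Applying each year's stopping only at the year end: 87-88%.
- A quarter of the effect kept after stopping, or a quarter of stopped patients back on drug: 88-89%.
- Half kept or half back on drug: about 92%.
- Stopping begins only after month 12: 91-92%.
- Discontinuers censored: 90.4%, but with only about 1,312 events and against the rule in Section 13.7.1.2.3.

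Under permanent stopping with full loss of effect, about a 27% reduction after year 1 would give 90%.

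**The case against.** The design figure is sound, and the miss lies in a parenthesis. The 1,600 events equal the plain requirement for HR 0.85, and a reader might take that as proof that the discontinuation allowance was left out. It is not: once 15% is the net effect, dilution is already inside it and the event requirement does not rise. This stands.

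The gap in effect is also small. Comparing event counts, the lag scenario gives a 13.4-13.6% reduction, but on that scale a constant HR of 0.85 itself gives only 14.3% (717 against 837). Like for like, on the hazard scale, it is about 14% against 15%.

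The strongest point is restart. Sections 11.1 and 11.3 ask that every attempt be made to restart study drug, and Section 8.3 asks patients who stop temporarily to resume. Sections 8.10 and 13.6.1.2 define a discontinuation as at least five consecutive days without drug, so the 10% is not said to be permanent. If 25-30% of stopped patients were back on drug, power would be about 88-90%. This stands as a reason not to present 84-85% as the power of the lag scenario without conditions. It does not rescue the text: Section 13.2 gives no restart share, and the equivalence cannot be reproduced without choosing one.

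A reader might also infer from Section 4.3 that the trial is really planned on the lag. That section says only that other lipid-modifying drugs took at least a year to show an effect, as a reason for a multiyear study. Section 13.2 puts the overall 15% first.

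**Conclusion.** The statement of equivalence is wrong as written. The 90% power applies to a net intention-to-treat hazard ratio of 0.85. Under the lag scenario, power is about 84-85% if 25% is an on-drug effect, stopping is permanent at 10% a year from randomization, stopped patients return to the placebo hazard, and accrual is uniform. It is 96-97% if nobody stops. Neither plain reading gives 90%. Values of about 88-92% are reachable, but only with unstated assumptions about restart, retained effect or timing.

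One might go on to infer that the trial is underpowered or that 8,500 per group is too few. The documents do not support that: the headline calculation reproduces, and the test, the alpha and the primary analysis are untouched. This is a misstatement of power for one scenario. It is worth correcting but is not a defect in the design.

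**What to change.** Amend Section 13.2 as follows:
- Delete *or equivalently*.
- State that 15% is the net intention-to-treat hazard reduction (HR 0.85, about 1,555-1,580 expected events, about 90% power).
- State whether 25% is a net or an on-drug effect.
- State the assumed timing of discontinuation, the assumed share of patients restarting, and the effect assumed to remain after stopping.
- Give the lag scenario's power on its own: about 84-85% under permanent stopping with full loss of effect, with the range under the other assumptions beside it. The 84-85% should appear as conditional on those assumptions, not as a single fact.

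This changes protocol wording only. Sample size, test and analysis stay as they are. The price is a less favourable stated power for the lag scenario.

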13.3 Study patient description

13.3.1 Disposition of patients

The number of randomized patients will be summarized by country and center using counts and percentages.

The number of patients either completing or permanently discontinuing the study drug period will be summarized using counts and percentages.

13.3.2 Clinical Trial Protocol deviations

All the following deviations will be summarized on the all randomized patient population:

- Inclusion or exclusion criteria not satisfied.
- Deviations related to the study drug administration
- Not permitted concomitant medications.

13.4 Data analysis considerations

13.4.1 Dataset analyzed

13.4.1.1 Treatment group considered for statistical analysis

For all efficacy and safety analyses, patients will be included in the treatment group to which they were originally allocated by the IVRS.

13.4.1.2 Populations to be analyzed

The intent-to-treat (ITT) population will be used for all efficacy and safety analyses. This will consist of all randomized patients irrespective of whether the patient actually received study drug or the patient's compliance with the study protocol, in the treatment group assigned by the IVRS system. A patient will be considered randomized as soon as a treatment kit number is assigned by IVRS.

13.4.1.3 General statistical approach

All statistical tests will be two-sided.

All summary tables for quantitative parameters will display mean, standard deviation, median, range (minimum and maximum), as well as number of missing data (if relevant). All summary tables for qualitative parameters will display counts, percentages and number of missing data if relevant.

Baseline data are defined as the last measurement performed before the first study drug intake.

13.4.2 General convention

13.4.2.1 General rules for handling of missing, unused or inconsistent data

In general, missing values will remain as missing, i.e., no attempt will be made to impute missing values and only observed values will be used in data analyses and presentations. Specific rules for handling missing efficacy data are described in [Section 13.7.1.2.1](#).

13.4.2.2 Other specific conventions

13.5 Demographic and baseline characteristics

13.5.1 Patient demographic characteristics, medical history and diagnoses

Baseline characteristics will be described using the ITT population. Demographics, medical history and other baseline variables will be summarized as appropriate to the type of data.

13.5.2 Previous medications

In order to further characterize the study population, the incidence of the use of selected medications (statins, antihypertensive agents, antidiabetic agents and antiplatelet agents) at the time of randomization will be summarized.

13.6 Investigational Product and concomitant therapy

13.6.1 Investigational Product

13.6.1.1 Extent of exposure

The duration of study drug treatment (accounting for permanent discontinuation) will be summarized. The number of patients on treatment over time will be summarized. The total patient years on study drug will also be calculated.

13.6.1.2 Measurement of treatment compliance

Treatment compliance for each patient will be calculated as the number of days study drug was actually taken (ie, number of days on treatment minus days of temporary discontinuation) divided by the number of days of follow-up, allowing for early permanent discontinuation of study drug when applicable. Study drug discontinuation is defined as a minimum of 5 consecutive days without study drug intake. The percentage of patients at least 80% compliant will also be reported.

13.6.2 Concomitant medication/therapy

The incidence of the use of selected concomitant medications (statins, antihypertensive agents, antidiabetic agents, and antiplatelet agents) will be summarized in each treatment group.

13.7 Efficacy/activity analysis

13.7.1 Primary efficacy variable(s)

13.7.1.1 Description of the primary variable(s)

The primary efficacy endpoint is the composite cluster of the first occurrence, over the duration of study (randomization to study end date inclusive), of the following adjudicated events:

- Any MI,
- Any stroke,
- Cardiovascular death

as validated by the CEC.

13.7.1.2 Primary analysis

13.7.1.2.1 Handling of dropouts or missing data

All randomized patients will be included in the primary ITT efficacy analysis. Patients not reaching the primary efficacy endpoint by the study end date, or before their last assessment for patients lost to follow-up, will be censored at the date of their last assessment visit.

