1.1 Study Flowchart

Evaluation	Treatment and follow-up																				
	VISIT	Baseline Visit	1M visit	3M visit	6M visit	9M phone call	12M visit	15M phone call	18M visit	21M phone call	24M visit	27M phone call	30M visit	33M phone call	36M visit	39M phone call ¹	42M visit ¹	45M phone call ¹	48M visit ¹	Final visit ^{2,3} (end of study)	
	Day	Day 1	D30 ±7	D90 ±14	D180 ±14		D360 ±14		D540 ±14		D720 ±14		D900 ±14		D1080 ±14		D1260 ±14		D1440 ±14	D1500 +30	
Design																					
Informed consent	X																				
Patient demographics	X																				
Medical / surgical history ⁴	X																				
Current medications	X																				
Smoking status	X																				
Inclusion criteria	X																				
Exclusion criteria	X																				
Physical examinations																					
Supine heart rate & blood pressure	X	X	X	X			X		X		X		X		X		X		X	X	
Physical exam ⁵	X			X			X		X		X		X		X		X		X	X	
Body weight	X			X			X		X		X		X		X		X		X	X	
Waist circumference	X			X			X		X		X		X		X		X		X	X	
Height	X																				
12-lead ECG	X																			X ⁶	
Randomization	X																				
Efficacy																					
Efficacy outcomes																					X
Treatment																					
IVRS call	X			X			X		X		X		X		X		X		X		
Study drug intake	X																				X
Study drug compliance			X	X	X		X		X		X		X		X		X		X		X
Concomitant medications			X																		X
Counseling ⁷	X																				

¹ If final visit has not been already performed.

² Final visit can occur between 33 and 50 months.

³ Visit may occur up to 30 days after, but never before, the study end date. However, only data up to the study end date should be recorded on CRF.

⁴ Including neurological and psychiatric history (scripted questions)

⁵ Including detailed neurological exam at baseline.

⁶ 12-lead ECG obtained at penultimate (next to last) visit

⁷ Dietary counseling, exercise counseling, and smoking cessation counseling, if appropriate.

Laboratory testing																		
Urinary pregnancy test ⁸	X																	
Hematology ⁹	X		X		X		X		X		X		X		X		X	X
Biochemistry ¹⁰	X		X		X		X		X		X		X		X		X	X
Safety																		
AEs ¹¹	X																	X

⁸ For women of childbearing potential only.

⁹ Hb, Ht, WBC-diff, platelets

¹⁰ ALT, AST, ALP, creatinine

¹¹ Including neurological and psychiatric AEs (scripted questions)

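### Event-free patients are censored at their last visit while events are counted to the study end date, which can bias the log-rank test if missed visits differ by arm

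*Protocol*

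**What the plan says.** Section 13.7.1.2.1 sets the censoring rule: patients without a primary event "will be censored at the date of their last assessment visit". The same sentence has a clause for lost patients, who are those not reaching the endpoint by the study end date "or before their last assessment for patients lost to follow-up".

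Section 13.7.1.2.3 sets the event rule: "all adjudicated events occurring from randomization to the study end date (inclusive) will be counted". Section 13.7.1.1 gives the same window. The resulting times are "analyzed (primary analysis) using a two-sided log-rank test".

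Several sections direct sites to learn endpoint status without a visit:
- Section 11.2, after withdrawal of consent, encourages investigators to "get information from the general practitioner, any other physician, or other medical-care provider". It also asks for one more contact when the study closes, "in order to obtain at least their vital status (dead or alive), as well as their stroke or MI status if possible".
- Section 11.3 repeats the request for status at the study end date.
- Section 12.3 schedules phone calls between visits. It also lets the final-visit form be completed late if information arrives after the 30-day window.

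Two further dates matter. On the final visit, footnote 3 of the flowchart (section 1.1) says "Visit may occur up to 30 days after, but never before, the study end date". For patients followed beyond the study for an adverse event, section 11.2 says of new events that "only those that occur up through the last visit should be recorded", although the paragraph before it runs recording to the study end date.

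**The concern.** The log-rank test needs each patient's time at risk to end for reasons unrelated to the outcome. Here the end of follow-up can depend on the outcome. Suppose a patient stops attending at month 12 and is traced at month 40. If an infarction at month 30 is found, the patient contributes an event at month 30. If no event is found, the patient is censored at month 12 and 28 months of known event-free time are lost. The event rate in such patients is inflated in both arms. If one arm has more of them, the inflation does not cancel.

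The direction depends on which arm misses more visits. More missed visits on rimonabant would hide benefit, and more on placebo would create apparent benefit. The protocol fixes this rule for the primary analysis, and section 13.1 makes the section the basis for the SAP, so it is not simply a detail left for later.

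**Working it through.** **1. The plan's own figures (section 13.2).** Placebo rate 3% per year, 17 months' accrual, 50 months in total, 8,500 per arm, 15% risk reduction taken as a hazard ratio (HR) of 0.85, two-sided 5%, 90% power, about 1,600 events.
- Schoenfeld: 4 × (1.960 + 1.282)² / (ln 0.85)² gives 1,592 events; Freedman gives 1,599.
- Power at 1,600 events: Φ(0.1625 × √1600 / 2 − 1.96) = Φ(1.29) = 90.2%.
- Expected events at hazard 0.03: 8,500 × (0.0985 + 0.0844) ≈ 837 + 717 = 1,554, power 89.3%.

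The design figures reproduce.

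**2. Size by hand.** Let D be the events counted in an arm and L those that fall after the patient's last visit. With a constant hazard, L/D is also about the share of observable time that the literal rule drops, so that arm's rate is inflated by about 1/(1 − L/D). Hence

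HR read ≈ true HR × (1 − L₀/D₀) / (1 − L₁/D₁), with 0 for placebo and 1 for rimonabant.

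- Visit loss 2% versus 4% per year, all traced: L₀ = 32 of 837, L₁ = 54 of 717. Factor 0.962 / 0.925 = 1.040; HR 0.85 reads as 0.884.
- Visit loss 1% versus 2% per year, half traced: L₀ = 8 of 829, L₁ = 14 of 704. Factor 0.990 / 0.980 = 1.010; HR 0.85 reads as 0.859.

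The values of L are simulation averages. The D values are the expected events, less the untraced late events in the half-traced case.

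**3. Simulation.** 8,500 per arm, placebo hazard 0.03, the protocol's visit schedule, true HR 0.85, 600 trials per row. The matched rule censors everyone at the last date status is known, capped at the study end date. HR is the log-rank-based estimate. Loss and tracing rates are assumptions.

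| Visit loss per year, placebo / rimonabant | No final visit | Traced | Literal: HR, power | Matched: HR, power |
|---|---|---|---|---|
| 1% / 1% | 3.4% / 3.4% | all | 0.850, 90% | 0.850, 90% |
| 1% / 2% | 3.4% / 6.7% | none | 0.849, 88.5% | 0.849, 88.5% |
| 1% / 2% | 3.4% / 6.7% | half | 0.861, 83% | 0.853, 88.5% |
| 1% / 2% | 3.4% / 6.7% | all | 0.866, 78.5% | 0.850, 88% |
| 2% / 4% | 6.7% / 12.9% | half | 0.867, 78.5% | 0.850, 88% |
| 2% / 4% | 6.7% / 12.9% | all | 0.880, 71% | 0.847, 92% |

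Monte Carlo error is about 0.002 on HR and 1 to 2 points on power. A separate simulation gave 0.858 for 1% versus 2% with half traced and 0.881 for 3% versus 5% with all traced. Another, with 300 trials per scenario, put power in that last case at about 67%, against 89% with matched censoring. A threefold difference in loss (2% versus 6%, half traced), run as a stress case, gave 0.887.

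With true HR 1.00, over the traced scenarios with twofold loss, two-sided rejection was 6.5% to 11.8% under the literal rule and 3.3% to 6.2% under the matched rule.

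**4. The other reading.** If events after the last visit are dropped for patients without a final visit, events and time match and the bias goes (HR 0.847 to 0.853 in the rows above). The cost is lost events: at 2% versus 4% with all traced, 32 + 54 = 86 of about 1,554, or 5.5%.

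**5. The other two date mismatches.** With no visit loss and 1% per year non-cardiovascular death, the final-visit window and the death-date gap leave the HR at 0.849 under both rules.

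**The case against.** The best defence is that the protocol does not require the biased rule. The lost-patient clause in section 13.7.1.2.1 can be read as stopping events and time together, and section 11.2 has the case report form for lost patients completed only to the last visit performed. Section 12.3 allows late completion of the final-visit form, so a traced event-free patient may in effect have a final assessment and not be cut back. Patients who only stop study drug, the 10% per year of section 13.2, stay on the visit schedule. Tracing is encouraged rather than guaranteed, so full tracing is a ceiling.

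Much of this stands. A reader might infer that the protocol mandates outcome-dependent censoring and that the result will be biased. The text does not support that: it allows two readings, and the bias needs both unequal visit loss and off-visit tracing. A reader might also infer that the 30-day final-visit window and the handling of non-cardiovascular deaths distort the result. They do not to any material degree, and footnote 3 limits recorded data to the study end date. Nor is a primary hazard ratio at issue: the primary analysis is a log-rank test, and Cox estimates appear only for subgroups (section 13.7.1.2.5). Hazard ratios here only express the size of the log-rank distortion.

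The defence still does not settle the matter. The harmless reading drops events that section 13.7.1.2.3 includes and wastes the tracing in sections 11.2 and 11.3. Section 12.3 does not say which date a late-completed form carries.

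**Conclusion.** The concern holds in a limited form. The censoring rule and the event rule use different windows for patients who stop visits but whose status is later learned. One reading biases the primary log-rank test against the arm with more missed visits. The other contradicts the event rule.

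On the literal reading, a true HR of 0.85 reads as about 0.86 at modest differential loss with half traced, and about 0.88 at 3% versus 5% per year with all traced. The corresponding power losses run from about 6 points to just over 20. With equal loss, or no off-visit tracing, there is no bias. These sizes rest on assumed loss and tracing rates, constant hazards, and tracing that does not depend on outcome.

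The final-visit window, the non-cardiovascular death date and the two recording cut-offs in section 11.2 are consistency points. Severity: moderate, should-fix.

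**What to change.** Replace the rule in section 13.7.1.2.1 with one window for events and time at risk:
- Censor event-free patients at the earliest of the study end date, the date of non-cardiovascular death, and the last date primary-endpoint status is known from any contact (visit, phone call, physician report or study-end check).
- Count events over that same window.
- Align sections 11.2, 13.7.1.2.1 and 13.7.1.2.3, including the last-visit wording in 11.2.

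Patients with vital status only need their own rule. Section 9.1.2.1.3 classes deaths of unknown cause as cardiovascular, so a patient found dead can become a primary event while one found alive is cut back. Simulated at 3% versus 5% per year, with a third to a half of events being cardiovascular deaths, that asymmetry alone gave an HR of 0.86 and power of 80% to 83%. Either count deaths found this way and carry those found alive to the vital-status date, or censor both at the last date infarction and stroke status was known. Name one as primary and the other as a sensitivity analysis.

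The cost is a short amendment, plus recording the date of every off-visit status contact. Section 12.3 mentions phone-call and contact forms, but the protocol does not say that physician-report dates are captured, so a form field may be needed. No extra patients or visits are required.
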